9.2 SETTING

9.2.1 Study sites

We will use administrative health insurance claims data from the Optum Research Database (ORD) for the period of October 1, 2013 through end of data availability (currently September 30, 2021). The ORD contains enrollment information, as well as fully-adjudicated medical claims and pharmacy claims for commercial enrollees and MAPD beneficiaries. In 2018, the ORD included 14.3 million commercial enrollees with medical and pharmacy benefits and 4.3 million beneficiaries with Medicare Part C (commonly referred to as the Medicare Advantage program). Medicare Advantage beneficiaries choose to receive all of their health care services through a provider organization in lieu of Medicare Part A/B coverage (commonly referred to as Medicare Fee for Service). These plans are referred to as MAPD when combined with Medicare Part D coverage. The average enrollment duration was 31.4 and 37.3 months for commercial enrollees and MAPD enrollees, respectively. Underlying information is geographically diverse across the United States and enrollees are fairly representative of the U.S. population. Medicare beneficiaries retain a single identifier within the system and can be tracked as they change plans, or as they disenroll and reenroll over time.

Claims for pharmacy services are typically submitted electronically by the pharmacy at the time prescriptions are filled. The claims history is a profile of all outpatient prescription pharmacy services provided and covered by the health plan. Pharmacy claims data include drug name, dosage form, drug strength, fill date, days of supply, financial information, and de-identified patient and prescriber codes, allowing for longitudinal tracking of medication refill patterns and changes in medications. Pharmacy claims are typically added to the research database within six weeks of dispensing.

Medical claims or encounter data are collected from all available health care sites (inpatient hospital, outpatient hospital, emergency department, physician's office, surgery center, etc.) for virtually all types of provided services, including specialty, preventive and office-based treatments. Medical claims and coding conform to insurance industry standards. Claims for ambulatory services submitted by individual providers, such as physicians, use the Health Care Financing Administration (HCFA)-1500 or Centers for Medicare and Medicaid Services (CMS)-1500 formats. Claims for facility services submitted by institutions, e.g., hospitals, use the Uniform Billing (UB)-82, UB-92, UB-04, or CMS-1450 formats. Medical claims include: multiple diagnosis codes recorded with the International Classification of Diseases, Ninth Revision, Clinical Modification (ICD-9-CM) and International Classification of Diseases, Tenth Revision, Clinical Modification (ICD-10-CM) diagnosis codes; procedures recorded with ICD-9-CM and ICD-10-CM procedure codes, Current Procedural Terminology (CPT), or Health care Common Procedure Coding System (HCPCS) codes; site of service codes; provider specialty codes; revenue codes (for facilities); paid amounts; and other information. Typically, facility claims do not include medications dispensed in hospital. Approximately six months following the delivery of services is required for complete adjudication of medical data.

NIS Protocol Page 17 of 36

Study number: 1199-0526 Document number: c41847952-01

Proprietary confidential information © 2023 Boehringer Ingelheim International GmbH or one or more of its affiliated companies

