The main outcome of our study will be incidence of dose reduction/interruption, calculated separately for pirfenidone and nintedanib. For each patient, average daily dose will be calculated in pre-specified time-periods (for example – the first 6 months, the first 12 months, and the average daily dose calculated separately in each month since drug initiation) (more details in section 2.6). Incidence of dose reduction/interruption will be defined as average daily dose not following the prescribing information (PI). According to the PI, the daily dose of pirfenidone is 2403 mg [13], hence the study will consider average daily dose less than 2165 mg (90% of PI dose) as dose reduction for pirfenidone [12]. For nintedanib, the daily dose allowed under prescriber information is 200 mg [14], hence less than 200 mg will be considered a dose reduction for nintedanib patients. As a secondary outcome, we will also assess drug discontinuation during first 6 and 12 months separately for pirfenidone and nintedanib and will be defined as a gap of at least 60 days in filling of prescription (a gap of 60 days after the prescription date + days of supply for the current prescription). In a sensitivity analysis, we will explore 30- and 90- days gap as a definition for drug discontinuation. As this is a descriptive study, assessment of the dose reduction and discontinuation for both drugs will be considered separately, and only descriptively, without any direct comparison between the two cohorts.

NIS Protocol Page 16 of 36

Study number: 1199-0526 Document number: c41847952-01

Proprietary confidential information © 2023 Boehringer Ingelheim International GmbH or one or more of its affiliated companies

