9.3.2 Outcomes

9.3.2.1 Primary outcome

The main outcome measure of our study is the incidence of dose reduction/interruption, calculated separately for each drug. For calculating the primary outcome, we will first need to calculate the average daily dose of pirfenidone and nintedanib after drug initiation (post-index period). Specific details of calculations are —

Average daily dose

Average daily dose for each patient will be calculated by taking the average of total drug intake (tablet strength * number of doses) during the time between index date to the date of drug discontinuation

```
Average \ Daily \ Dose \\ = \frac{\sum_{0}^{n}(Tablet \ Strength*number \ of \ tablets \ in \ a \ Rx \ fill)}{Time \ of \ follow - up \{(Date \ of \ discontinuation) - Index \ Date\}} Where n = number of fills a patient has received for pirfenidone/nintedanib
```

- We will calculate average daily dose of pirfenidone and nintedanib separately for each month in post-index period (month 1 to 12) and will also calculate for cumulative periods of 6 months and 12 months. For all calculations, censoring events will be taken into account, with patient censored at the date of drug discontinuation, or end of 12 months.
- Six and twelve months average daily dose categories For the average daily dose calculations in cumulative periods, we will be dividing the patients in following 4 categories
 - 1) Dose strength less than 50%
 - 2) Dose strength between 51% to 66%
 - 3) Dose strength between 67% to 90%
 - 4) Dose strength above 90%

Incidence of Dose Reduction and/or temporary dose interruption

Once average daily dose is calculated for each month post-index (month 1 to 12), incidence of dose reduction/interruption will be calculated as presence of average daily dose $\leq 90\%$ dose strength (for pirfenidone) or $\leq 66.67\%$ dose strength (for nintedanib), as per the PI [12 – 14]. Patients will be required to have the dose reduction for at least for 60 days, to make sure that the dose reduction is not temporary.

In a sensitivity analysis, we will also evaluate temporary dose reductions, i.e., dose reduced to below the above defined dose strength only for 1 month.

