Inpatient length of stay	A count of the number of days (length of stay) a beneficiary was hospitalized in an inpatient facility during the baseline period. Length of stay for each inpatient hospitalization claim will be calculated as the arithmetic difference between each claim's from and through dates.	
Total inpatient spending	A continuous, non-negative variable representing the total amount paid by all parties for all inpatient hospitalizations (for any cause) as reported in inpatient facility claims during the baseline period.	
Outpatient facility use and spending		
Any outpatient visit	A binary indicator for whether a beneficiary had at least one claim for services provided by an outpatient facility for any cause during the baseline period.	
Outpatient visit count	A count of the number of unique dates with an outpatient facility for any cause claim a beneficiary had during the baseline period.	
Total outpatient spending	A continuous, non-negative variable representing the total amount paid by all parties for outpatient facility claims during the baseline period.	
Medical spending		
Total Medical spending	A continuous, non-negative variable representing the total amount paid by all parties all medical claims during the baseline period, calculated as the sum of the allowed amounts on each claim.	
OOP Part B spending	A continuous, non-negative variable representing the total amount paid out-of-pocket by the beneficiary for all medical claims during the baseline period.	
Total spending		
Total spending	A continuous non-negative variable representing the total amount paid by all parties for all medical	

NIS Protocol Page 23 of 36

Study number: 1199-0526 Document number: c41847952-01

Proprietary confidential information © 2023	Boehringer Ingelheim International	I GmbH or one or more of its affiliated companies

Variable	Description	
	and pharmacy claims during the baseline period and will be calculated as the sum of total pharmacy and total medical spending.	
Other use		
Any ED visit	A binary indicator for whether a beneficiary had at least one emergency department visit during the baseline visit.	
ED visit count	A count of the number of unique dates with an emergency department visit that a beneficiary had during the baseline period.	

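### No rule handles post-index hospital days in average daily dose: short stays can distort the monthly doses and the one-month sensitivity analysis, and less often the 60-day primary outcome.

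*Combined protocol and SAP*

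**What the plan says.** **Numerator.** Section 9.2.1 describes the pharmacy data: "The claims history is a profile of all outpatient prescription pharmacy services provided and covered by the health plan". The formula in Section 9.3.2.1 sums tablet strength times number of tablets over these fills. On drug given during a stay, Section 9.2.1 says: "Typically, facility claims do not include medications dispensed in hospital".

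**Denominator.** Section 9.3.2.1 states: "Average daily dose for each patient will be calculated by taking the average of total drug intake", taken "during the time between index date to the date of drug discontinuation". The calculation is made for each of months 1 to 12 and for the cumulative 6 and 12 months, "with patient censored at the date of drug discontinuation, or end of 12 months". Hospital stays are not mentioned.

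**Cut-offs.** Section 9.1 takes "average daily dose less than 2165 mg (90% of PI dose) as dose reduction for pirfenidone"; for nintedanib, "less than 200 mg will be considered a dose reduction for nintedanib patients". Section 9.3.2.1 words the same limits as at or below 90% and at or below 66.67% of full dose.

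**Persistence.** Section 9.3.2.1 requires the reduction to last at least 60 days. Its worked example has a patient below the limit throughout months 2 and 3. Reductions of one month are counted only in a sensitivity analysis.

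**Use of inpatient days.** They appear only as a baseline covariate. Section 9.3.3 gives the method: "Length of stay for each inpatient hospitalization claim will be calculated as the arithmetic difference between each claim's from and through dates".

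**Limitations.** Section 9.9 says in general terms that a dose derived from fills may differ from actual intake, and that reduction and interruption cannot be told apart. It does not name hospital stays.

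**The concern.** The plan records a gap in its data source and then defines its main outcome as a ratio exposed to that gap. If the hospital supplies the antifibrotic, the patient saves tablets at home and refills later. Those days stay in the denominator with no drug against them, and a fully treated patient appears to have taken less.

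The pirfenidone limit leaves about 10% of room in a month, so a few days matter. Section 7 says the study may show that patients miss the full benefit of pirfenidone through sub-optimal dosing, and for full-dose patients this artefact would add to that finding. Hospitalised patients are plausibly the sicker ones. The contingent propensity matching in Section 9.7.2 uses pre-index measures only, so it cannot remove an error created by stays during follow-up.

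**Working it through.** **The plan's own limits.** 0.90 × 2403 = 2162.7 mg, and 2165/2403 = 90.1%, so the pirfenidone limit reproduces to within 0.1 percentage point. For nintedanib, 200/300 = 66.67%.

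**Model.** Average over a period of M days = usual daily dose × (M − L)/M, where L is the number of days by which a stay delays the refill. Assumptions not in the documents: the hospital supplies the drug, the refill slips day for day, there is no stockpile, adherence is otherwise full, and tablets are spread over supply days. A 30-day month is used unless stated.

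**Pirfenidone, one month.**
- L = 3: 27/30 × 2403 = 2162.7 mg (90.0%). This is low under both wordings of the limit.
- 28-day month, L = 3: 25/28 × 2403 = 2145.5 mg, low.
- 31-day month: L = 3 gives 28/31 × 2403 = 2170.5 mg, not low; L = 4 gives 27/31 × 2403 = 2092.9 mg, low.
- L = 7: 23/30 × 2403 = 1842.3 mg (76.7%).

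A stay can straddle two months. Over the 30 possible start days, a 3-day stay produces a low month in 28 (93.3%), a 4-day stay in 29 (96.7%), and a stay of 5 days or more in all 30.

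**Pirfenidone, 60-day primary outcome read as two whole low months.** Each month must lose at least 3 days, so one stay must put 3 or more days on each side of a month boundary. That allows L − 5 placements out of 30 for the lengths shown:

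| Stay (days) | Qualifying placements |
|---|---|
| 1 to 5 | 0 of 30 |
| 6 | 1 of 30 (3.3%) |
| 7 | 2 of 30 (6.7%) |
| 10 | 5 of 30 (16.7%) |
| 14 | 9 of 30 (30.0%) |

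Separate stays of 3 or more days in two consecutive months also qualify.

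**The same outcome read as a 60-day average.** 6 days suffice: 54/60 = 90.0%. A 7-day stay gives 53/60 = 88.3%.

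**Cumulative dose categories.** Leaving the top category takes 18 days in 180 (162/180 = 90.0%) or 37 in 365 (328/365 = 89.9%).

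**Nintedanib, one month.**
- At 300 mg/day, L = 10 gives 20/30 × 300 = 200 mg. That is low under the wording of Section 9.3.2.1 but not under Section 9.1, where L = 11 is needed (19/30 × 300 = 190 mg).
- At 200 mg/day, L = 1 gives 29/30 × 200 = 193.3 mg, low. Under the wording of Section 9.3.2.1 this patient is counted even without a stay, since 0.6667 × 300 = 200.01 mg.

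**Allocation of fills.** The plan does not say how a fill is spread over months. When tablets were instead credited to the month of the fill date, with 30-day fills and the second and later fills delayed by 3, 5 or 7 days, no month was low.

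**After removing inpatient days from the denominator.** A 7-day stay gives (23 × 2403)/23 = 2403 mg instead of 1842.3 mg. The 3-, 4- and 5-day cases also return to 2403 mg, from 2162.7, 2082.6 and 2002.5 mg.

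**The case against.** The strongest reply is that the plan already guards its main outcome with the 60-day requirement. This stands in large part. On the reading shown in the plan's own example, one stay of 5 days or less can never count, and a 7-day stay fails in 28 of 30 placements. A reader might infer from the monthly arithmetic that short stays by themselves generate primary-outcome reductions on pirfenidone. The documents do not support that.

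A reader might also infer that the error works against pirfenidone, given 10% of room against 33%. That contrast holds only for nintedanib at 300 mg/day. At 200 mg/day, which Section 9.1 treats as within label, there is no room at all. The dose mix is not given, so neither the direction nor the size of any difference between drugs can be stated.

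The mechanism is also assumed. The sentence on facility claims is general, is qualified as typical, and does not speak of these two drugs. If patients use their own supply or refill on schedule, there is no deficit. If treatment is withheld in hospital, the low average is a true interruption, which the outcome is meant to include. All of this stands, and it argues against replacing the primary definition.

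Finally, Section 9.9 already concedes that fills may not equal intake. That is only a partial answer: it does not name hospital stays and gives no way to judge their effect.

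**Conclusion.** The gap is real and of modest importance. Drug given in hospital is typically invisible, the days remain in the denominator, and no rule deals with them. Under the stated assumptions, 3 inpatient days (4 in a 31-day month) take a full-dose pirfenidone patient to or below the limit for that month. The monthly doses and the one-month sensitivity analysis are therefore the results most exposed.

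The primary outcome is reached less often. It takes a single stay of at least 6 days across a month boundary, or stays of 3 or more days in two consecutive months. If the 60 days are averaged, 6 days are enough. Nintedanib is affected too, so the problem is not specific to one drug.

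The documents give no hospitalisation rate during follow-up, so the effect on incidence cannot be estimated. The figures show what a stay can do to one patient, not how many patients are affected.

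**What to change.** Keep the primary definition. Add to Section 9.3.2.1 a sensitivity analysis that subtracts post-index inpatient days from the monthly and cumulative denominators and extends the refill-gap clock by the same days. Identify the days from claim from and through dates, as Section 9.3.3 does for baseline length of stay. Report dose reduction and discontinuation both ways. State how fills are allocated to months, because the size of the effect depends on it, and name hospital stays in Section 9.9.

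The cost is some programming on inpatient claims already in the data source. The baseline method must be run on follow-up claims and split at month boundaries.

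The downside is that the adjusted analysis assumes treatment continued in hospital. It hides true in-hospital interruptions, and it overstates dose for a patient who used home supply (30/27 = 111% after a 3-day stay at full dose). The two analyses should therefore be read as bounds: the primary as the high count of reductions, the adjusted one as the low count.

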9.2.2 Study population

For the primary study objective, patients included in the cohort need to meet the following criteria:

- Presence of at least one pirfenidone or nintedanib prescription during the identification period (the date of first prescription for pirfenidone/nintedanib is the index date)
- Evidence of IPF: patient with at least one inpatient or two outpatient claims (>14 days apart) with a diagnosis code for IPF (ICD-10-CM: J84.112; ICD-9-CM: 516.31) during the study period (10/01/2013 to 09/30/2022)
- At least 18 years old at the index date
- Have at least 12 months of continuous enrollment in the health plan during pre-index period, and at least 6 months of continuous enrollment in post-index period (for 12-months analysis, patients would be required to have 12 months post-index continuous enrollment)

Exclusion criteria include the following:

- Any history of lung transplant during the 12-months pre-index/baseline period
- Any claims for a skilled nursing facility, a long-term care facility or hospice care during the 12-month pre-index period
- Evidence (≥2 ICD-9-CM or ICD-10-CM diagnostic codes on different dates) of non-IPF chronic fibrosis ILD or connective tissue diseases during the 12-months pre-index period. The following conditions will be excluded: autoimmune, or connective tissue diseases (i.e., rheumatoid arthritis (RA), systemic lupus erythematosus (SLE), dermatopolymyositis, systemic sclerosis, Sjogren's syndrome, and mixed connective tissue disease (CTD)), sarcoidosis, and hypersensitivity pneumonitis).
- Missing demographic information (i.e., age or sex)

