9. RESEARCH METHODS

9.1 STUDY DESIGN

This study will be a retrospective cohort, descriptive study of patients with idiopathic pulmonary fibrosis (IPF). Patients with IPF who initiated either pirfenidone or nintedanib between October 2014 to September 2021 will be identified. The study will use data from the Optum Research Database (ORD), a claims database containing approximately 14 million commercial enrollees and 4 million Medicare-advantage enrollees. The date of the first prescription of either pirfenidone or nintedanib will be assigned as index date. Two separate cohorts will be created - 1) pirfenidone initiators, and 2) nintedanib initiators, and all outcomes will be assessed in the 12 months post-index period. A 12-month time-period prior to the index date will be used as the baseline period for determining the characteristics of patients in both cohorts. To allow for a 12-months baseline and follow-up periods for all patients, the span of data will be from 10/01/2013 to 09/30/2022. (Figure 1)

[figure not shown]

Figure 1 Study Design Schematic

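### The IPF inclusion criterion can be met by claims made up to 8 years after the index date, and no sensitivity analysis tests the effect

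*Combined protocol and SAP*

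**What the plan says.** Section 9.1 defines the target population: "Patients with IPF who initiated either pirfenidone or nintedanib between October 2014 to September 2021 will be identified". Section 9.2.2 sets the anchor: "the date of first prescription for pirfenidone/nintedanib is the index date".

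IPF itself is established in section 9.2.2 by "patient with at least one inpatient or two outpatient claims (>14 days apart"), the claims being ones "with a diagnosis code for IPF (ICD-10-CM: J84.112; ICD-9-CM: 516.31) during the study period (10/01/2013 to 09/30/2022"). That window is fixed in calendar time. No section requires an IPF claim on or before index, or within a stated interval of it.

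The neighbouring criteria are tied to index. Age is taken at the index date. The enrolment rule reads "Have at least 12 months of continuous enrollment in the health plan during pre-index period, and at least 6 months of continuous enrollment in post-index", with 12 months after index for the 12-month analysis. The transplant and the institutional or hospice care exclusions look at the 12 months before index. So does the exclusion for evidence (at least two codes on different dates) "of non-IPF chronic fibrosis ILD or connective tissue diseases during the 12-months pre-index period".

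The limitations in section 9.9 do not mention post-index diagnoses. The planned sensitivity analyses vary the discontinuation gap (30 and 90 days) and the duration of dose reduction (one month). None varies the IPF criterion.

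**The concern.** The study describes what happens to patients with IPF after they start a drug, so the cohort should be identifiable at the start. Under this rule, membership can depend on what is recorded later. Three consequences follow.

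- **Population.** Some patients may have had no recorded IPF at initiation.
- **Asymmetry.** An IPF code after index can bring a patient in, but repeated codes for another fibrotic lung disease after index cannot take a patient out.
- **Selection.** A patient who lacks sufficient earlier codes must stay alive, enrolled and in contact with care long enough to collect them. How much calendar time is available for that depends on the index date.

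The reported percentages are the study's result, and cohort membership sets their denominators.

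**Working it through.** No sample-size or power figure is involved, so the check is calendar arithmetic.

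**Inputs.** IPF claims window 10/01/2013 to 09/30/2022 (section 9.2.2). Index dates October 2014 to September 2021 (section 9.1), taken as 10/01/2014 to 09/30/2021. Enrolment at least 12 months before and 6 or 12 months after index (section 9.2.2). Average enrolment 31.4 months for commercial and 37.3 months for Medicare Advantage members (section 9.2.1).

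**Reproducing the plan's data span.** Section 9.1 states: "To allow for a 12-months baseline and follow-up periods for all patients, the span of data will be from 10/01/2013 to 09/30/2022". Earliest index minus 12 months: 10/01/2014 − 12 months = 10/01/2013. Latest index plus 12 months: 09/30/2021 + 12 months = 09/30/2022. Both agree with the plan.

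**Splitting the claims window at index.** Pre-index part = index date − 10/01/2013. Post-index part = 09/30/2022 − index date.

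| Index date | Before index (years) | After index (years) | Total (years) |
|---|---|---|---|
| 10/01/2014 | 1.00 | 8.00 | 9.00 |
| 01/01/2016 | 2.25 | 6.75 | 9.00 |
| 01/01/2018 | 4.25 | 4.75 | 9.00 |
| 01/01/2020 | 6.25 | 2.75 | 9.00 |
| 09/30/2021 | 8.00 | 1.00 | 9.00 |

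The total is the same for everyone (ratio 1.0). The post-index part differs by 8.00 / 1.00 = 8.0 between the extreme dates. Between the midpoints of the first and last index calendar years it differs by 7.87 / 1.37 = 5.7.

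**Allowing for enrolment.** These are calendar maxima; claims are seen only while a patient is enrolled. Assume enrolment equal to the stated averages, with exactly 12 months spent before index:

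- commercial: 31.4 − 12 = 19.4 months after index; 19.4 / 12 = 1.6
- Medicare Advantage: 37.3 − 12 = 25.3 months after index; 25.3 / 12 = 2.1

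The divisor is the 12 months open to the latest index date. The averages describe all enrollees rather than this cohort, so 1.6 to 2.1 is illustrative.

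**A window anchored to index.** With the 12 months before index through the index date, the window is 366 days for index 10/01/2014 and 366 days for index 09/30/2021. The ratio is 1.0, no future claims are used, and the enrolment rule already guarantees that the window is observed.

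**A date to reconcile.** Section 9.2.1 gives data "through end of data availability (currently September 30, 2021"), whereas the abstract and sections 9.1, 9.2.2 and 9.4 give September 30, 2022. With the earlier end date, the post-index part would run from 7.00 years to 0.

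**The case against.** The strongest case for the plan has four parts.

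1. **The drugs point to IPF.** Section 7 describes both as approved for IPF, so a later code in a treated patient may confirm existing disease. Searching the full data span trades specificity for sensitivity. This stands as a reason to keep the rule as primary. It does not remove the need for a check, because the protocol does not treat the prescription as sufficient: it requires IPF codes and excludes other diagnoses.
2. **Selection on follow-up exists anyway.** All outcomes fall within 12 months of index, and everyone must be enrolled for 6 or 12 months after it. Qualifying claims can accrue within that period. This stands in part: the additional selection applies only to patients whose qualifying claims come later still.
3. **The study is descriptive.** No direct comparison of outcomes between drugs is planned, and index year is reported and would enter the propensity score if matching is done. This lowers the stakes but does not settle who belongs in each denominator.
4. **Restricting to claims on or before index is no cure by itself.** This stands. Without a fixed look-back, the calendar opportunity would be 1 year for the earliest index date and 8 for the latest, which reverses the inequality.

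A reader might also infer that the opportunity to qualify differs 8-fold by index year. The documents do not support that. The criterion accepts claims before and after index, the total calendar window is 9 years for all, and the 8-fold figure describes only its post-index part at the two extreme dates.

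**Conclusion.** The point holds as a gap in the cohort definition that is cheap to test. Membership can depend on claims up to 8 years after initiation. The post-index part of the window ranges from 8.00 years to 1.00 year by index date, and neither section 9.9 nor any sensitivity analysis addresses this. The figures assume index dates from 10/01/2014 to 09/30/2021 and data through 09/30/2022.

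Two further inferences are tempting but unsupported. One is that the rule biases results towards persistence. Patients who stay on treatment may collect more IPF-coded visits, but someone who stops in month 2 can still qualify later. The direction is therefore plausible rather than shown, and the size cannot be derived. The other is a count of affected patients from the feasibility total of 1,979 + 2,559 = 4,538. Section 9.5 gives that total for 10/2014 to 12/2020 without saying which criteria were applied, and no section gives the share qualifying only after index.

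**What to change.** 1. Keep the current IPF rule for the primary analysis if the sponsor wishes. Pre-specify a sensitivity analysis of both the dose-reduction and the discontinuation outcomes, restricted to patients who meet the IPF criterion in one fixed window anchored to index, equal for all patients and inside the guaranteed enrolment. An example is the 12 months before index through the index date, optionally with a short fixed post-index allowance for coding lag. Such an allowance still uses some future information, but equally for everyone.
2. Report, by drug and index year, how many patients qualify only on claims after that window.
3. Add to section 9.9 that post-index claims can establish IPF and that the exclusion for other fibrotic lung or connective tissue disease does not look beyond index.
4. Reconcile the end of data in section 9.2.1 with the other sections.

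The cost is one date filter, a repeat of the outcome tables and a few sentences of text. No new data are needed. The downside is a smaller cohort in the sensitivity analysis, by an amount that the documents do not allow to be computed.
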